During the conduct of the trial, the observed exposure was much lower (factor of 11 to 19) than predicted. The prediction of the efficacious dose was updated to 700 mg (range 600 to 800 mg). Based on the accumulated safety and PK data, the SMC recommended to add 2 additional SAD cohorts of 1,000 mg and (dependent on SMC review) 1,500 mg. Due to observations of transient, increases in liver enzymes above ULN in 4 of 8 subjects (one subject Grade 2 ALT and Grade 1 AST, two subjects Grade 1 for both ALT and AST, and one subject Grade one for ALT – according to Toxicity Grading Scale for healthy volunteers) of the 1,000 mg SAD cohort, the SMC decided to dose the next cohort with an intermediate dose of 1,250 mg.

In case no clinically significant deviations of safety parameters or appearance of any moderate/severe IMP-related TEAEs are observed, the SMC may decide to explore higher doses.

It is envisaged to explore a dose (exposure) up to around 2,400 mg, assuming 3 times the highest anticipated therapeutic dose (exposure) of 800 mg, if feasible without jeopardizing the safety of the subjects in the study.

The SMC will convene at an appropriate time to allow for the compilation of the required data for review. The interval between the completion of IMP administration in one cohort and the initiation of IMP administration in the next cohort of subjects will therefore be minimally 25 days. This will allow sufficient time for an SMC review and the final decision to be communicated to the trial site. Initiation of a higher-dose cohort will only occur if the previous dose level was deemed to be generally safe and well-tolerated and is predicted not to exceed the maximum exposure (see Section 5.5).

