5.3.2 Exclusion Criteria

5.3.2.1 Part A, Part B, and Part C

1. History or presence of clinically relevant respiratory, gastrointestinal, renal, hepatic, hematological, lymphatic, neurological, cardiovascular, psychiatric, musculoskeletal, genitourinary, immunological, dermatological, connective tissue diseases or disorders.
2. History of any malignancy except surgically cured skin cancers.
3. History of relevant drug hypersensitivity, ascertained or presumptive allergy/hypersensitivity to the active drug substance and/or formulation ingredients; history of serious allergic reactions leading to hospitalization or any other allergic reaction in general, which the Investigator considers may affect the safety of the subject and/or outcome of the trial.
4. History of alcoholism or drug abuse.
5. Liver functions tests:
 - a. above the laboratory reference range the day before IMP administration (Day -1) for Part A and Part B
 - b. $\geq 3 \times$ ULN for Inoculum Day 8 in Part C.
6. Creatinine clearance < 90 mL/min as estimated using the Cockcroft and Gault equation at Screening.
7. Semi-supine BP $> 140/90$ mmHg at Day -1 (this may be repeated once).
8. Electrocardiogram shows a QT interval corrected for heart rate according to Fridericia's formula (QTcF) > 450 ms, PR > 210 ms, QRSD > 120 ms at Screening and predose.
9. Consumption of an average weekly intake of > 14 drinks/week for men or > 7 drinks/week for women. One drink is equivalent to 12 g alcohol = 5 ounces (150 mL) of wine or 12 ounces (360 mL) of beer or 1.5 ounces (45 mL) or 80-proof distilled spirits.
10. Positive for hepatitis B surface antigen, hepatitis B core antibody, hepatitis C antibody or human immunodeficiency virus (HIV) I and II tests at Screening.
11. Positive for drugs of abuse, nicotine/cotinine or alcohol on Screening or (each) admission.
12. Use of any investigational drug in any clinical trial within 90 days from the last administration, or on extended follow-up in a clinical trial, even if the last administration of an IMP was > 90 days ago.

13. Donation or loss of more than 450 mL of blood in the 90 days prior to Screening.
14. Excessive consumption of xanthine-containing food or beverages (> 5 cups of coffee per day or equivalent) or inability to stop consuming caffeine, from 48 hours prior to IMP administration until 48 hours after IMP administration.

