- Recovered without sequelae
- Recovered with sequelae
- Ongoing
- Fatal
- Unknown.

In case of a fatality, the cause of death is considered as the SAE, and the death is considered as its OUTCOME.

Abnormal Laboratory Findings and Other Abnormal Investigational Findings

Abnormal laboratory findings and other abnormal investigational findings should not be reported as AEs unless they are associated with clinical signs and symptoms, lead to treatment discontinuation or are considered otherwise medically important by the Investigator. If a laboratory abnormality fulfills these criteria, the identified medical condition must be reported as the AE rather than the abnormal value itself.

Serious Adverse Events

An SAE is any untoward medical occurrence that at any dose:

- Results in death
- Is life-threatening. (Note: The term “life-threatening” refers to an event in which the subject is at risk of death at the time of the event, not an event that hypothetically might have caused death if it was more severe)
- Requires inpatient hospitalization or prolongs an existing hospitalization
- Results in persistent or significant disability or incapacity
- Is a congenital anomaly or birth defect

- Is otherwise considered to be medically important. (Note: Important medical events that may not result in death, be life-threatening, or require hospitalization may be considered as SAEs when, based upon appropriate medical judgment, they may jeopardize the subject or may require medical or surgical intervention to prevent one of the outcomes listed above. Examples of such events include allergic bronchospasm requiring intensive treatment in an emergency room or at home, blood dyscrasias or convulsions that do not result in inpatient hospitalization, or the development of drug dependency or drug abuse).

For the purposes of reporting, any suspected transmission of an infectious agent via an IMP/inoculum is also considered an SAE and should be reported in an expedited manner, as described in Section 7.4.1.4.

Events that Do Not Meet the Definition of an SAE

Elective hospitalizations to simplify trial treatment or trial procedures (for example, an overnight stay to monitor initiation of treatment with the IMP is not considered an SAE. However, all events leading to unplanned hospitalizations or unplanned prolongation of an elective hospitalization (for example, undesirable effects of any administered treatment) must be documented and reported as SAEs.

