Events Not to Be Considered as AEs/SAEs

Medical conditions present at the initial trial visit that do not worsen in severity or frequency during the trial are defined as Baseline Medical Conditions, and are not to be considered AEs.

Adverse Events of Special Interest

The assessments to be performed for assessment of AESIs is detailed in Section 7.4.4.7.

The following are identified as AESIs in this trial:

- Vomiting or diarrhea
- Liver enzyme elevations (ALT/AST/Bilirubin)
- Cutaneous reactions (local tolerability CRF for severity of redness, swelling, induration, bruising, and itching)
- Photosensitivity/light sensitivity
- Pregnancy in a female partner of a male subject.

AESIs for monitoring should be reported following the procedure for an SAE described in Section 7.4.1.4.

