7.4.4.7 Specific Planned Assessments or Adverse Events of Special Interest

- Vomiting, diarrhea. In case of vomiting subjects should not be re-dosed and they should be kept in the trial, however the Investigator can decide whether to schedule the final Follow-up visit earlier
- Liver enzymes (ALT/AST/Bilirubin)
- Cutaneous reactions (local tolerability CRF for severity of redness, swelling, induration, bruising, and itching)
- Photosensitivity/light sensitivity
- Pregnancy in a female partner of a male subject. Any subject's female partner who becomes pregnant during the trial or in the following 20 weeks after the last dosing should be followed through delivery or termination of the pregnancy. Pregnancy is reported to the Sponsor by completion of the pregnancy form.

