#### 15.1.1 All Adverse Events

Treatment-emergent AEs will be summarized by dose and overall in tables with:

 The number and percentage of subjects with any TEAE, any IMP-related TEAE, any serious TEAE, any IMP-related serious TEAE, any Grade ≥3 TEAE, any IMP-related Grade ≥3 TEAE, any AEs of special interest (AESI), any TEAE leading to death, any IMP-related TEAE leading to death, any TEAE leading to study discontinuation

- The number and percentage of subjects with at least one TEAE by SOC and PT
- The number and percentage of subjects with at least one TEAE by worst grade, SOC, and PT
- The number and percentage of subjects with at least one IMP-related TEAE by SOC and PT
- The number and percentage of subjects with at least one TEAE by PT only, sorted in decreasing incidence overall
- The number and percentage of subjects with non-serious TEAEs by SOC and PT
- The number and percentage of subjects with at least one AESI recorded by SOC and PT.

Unless otherwise stated, AEs will be displayed with SOC terms and PTs within each SOC term sorted alphabetically.

For determining incidence counts, within each level of TEAE term, if a subject experiences more than one occurrence, the subject will only be counted once for that TEAE.

If an AE is reported for a given subject more than once during treatment, the worst severity and the worst relationship to study treatment will be tabulated.

Adverse events related to IMP are those events with relationship missing, unknown or yes.

In case a subject had events with missing and non-missing severity, the maximum non-missing severity will be displayed.

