## 15.2.3 Other Significant Adverse Event

The following will be considered as AESIs in this study:

Vomiting or diarrhea

- Liver enzyme elevations (alanine aminotransferase [ALT], aspartate aminotransferase [AST], bilirubin)
- Cutaneous reactions (local tolerability measured by severity of redness, swelling, induration, bruising, and itching)
- Photosensitivity/light sensitivity
- Pregnancy in a female partner of a male subject.

These AESIs will be summarized by SOC and PT, as applicable, as specified in Section 15.1.1.

For Part C, the malaria clinical score for treatment initiation will be listed and summarized by dose.

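### The liver-enzyme AESI has no laboratory criterion, its relation to the laboratory-finding rule in protocol 7.4.1.1 is not stated, and the SAP counts only what was recorded.

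*Protocol*

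**What the plan says.** **The AESI.** Protocol 7.4.1.1 lists "Liver enzyme elevations (ALT/AST/Bilirubin" (closing bracket omitted here and in the next two quotes). Section 7.4.4.7 repeats the analytes, "Liver enzymes (ALT/AST/Bilirubin", and SAP 15.2.3 has "Liver enzyme elevations (alanine aminotransferase [ALT], aspartate aminotransferase [AST], bilirubin". None of the three gives a multiple of ULN, a grade, a change from baseline or a confirmation rule. Multiples of ULN appear in the withdrawal criteria (5.5.1, 5.5.2) and the Part C entry limit (5.3.2.1), but none is tied to the AESI. A nonserious AESI must be reported within 24 hours (7.4.1.4).

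**The laboratory-finding rule.** Also in 7.4.1.1: "Abnormal laboratory findings and other abnormal investigational findings should not be reported as AEs unless they are associated with clinical signs and symptoms", or they "lead to treatment discontinuation or are considered otherwise medically important by the Investigator". A finding that qualifies is reported as the underlying condition, not as the value. The general definition in the same section allows an abnormal laboratory finding to be an AE. Section 7.4.1.2 treats nonserious AESIs as a subset of AEs.

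**The counting.** SAP 15.1.1 plans "The number and percentage of subjects with at least one AESI recorded by SOC and PT". SAP 15.3 plans descriptive statistics, change from baseline, box plots and listings of abnormal results.

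**What has been seen.** Protocol 5.2.2 reports transient "increases in liver enzymes above ULN in 4 of 8 subjects" at 1,000 mg, after which the Safety Monitoring Committee (SMC) chose an intermediate next dose. Part A and B subjects are excluded if liver tests are "above the laboratory reference range the day before IMP administration (Day -1) for Part A and Part B". Part C uses a limit of 3 x ULN on Inoculum Day 8.

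**The concern.** The liver AESI is itself a laboratory value, yet the rule governing laboratory values asks for something more before an AE is recorded, and then asks for a condition instead of the value. Two investigators with the same ALT series could record different numbers of AESIs and both be within the text.

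This matters because a Part A primary endpoint is the incidence of clinically significant laboratory abnormalities, with ALT and AST named (protocol 8.3.1, SAP section 5). Under the SAP, the only counts by dose of subjects with liver elevations come from recorded events in the AESI and TEAE tables. The dose relation of a laboratory signal already seen in the trial would therefore be tabulated through case-by-case judgement. Expedited AESI reporting depends on the same unresolved choice.

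**Working it through.** **1. Reproduce the plan's figure.** Protocol 5.2.2 breaks the 1,000 mg cases down as one subject with Grade 2 ALT and Grade 1 AST, two with Grade 1 for both, and one with Grade 1 ALT. 1 + 2 + 1 = 4 of 8. The figure reproduces.

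**2. Apply the laboratory-finding rule to an asymptomatic rise in Part A.**
- Symptoms: not met, by assumption. Section 5.2.2 gives no symptom information.
- Treatment discontinuation: cannot apply, because 5.5.1 says a subject cannot be withdrawn from treatment after the single Part A dose.
- Medically important: Investigator judgement, with no threshold stated.

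For such a subject, recording rests on the third limb alone.

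**3. Count the same eight subjects under different readings.**

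| Reading | Recorded as AESI |
|---|---|
| Any value above ULN (all four were Grade 1 or higher) | 4/8 = 50.0% |
| Grade 2 or higher | 1/8 = 12.5% |
| Grade 3 or higher | 0/8 |
| Laboratory-finding rule, none of the four symptomatic or judged important | 0/8 |

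Because judgement is made subject by subject, any count from 0 to 4 is reachable.

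**4. Convert to the table the SAP would print.** Allocation is 6 active to 2 placebo (5.2.2), and placebo is pooled across cohorts within a part (SAP section 9). The dose column therefore has 6 subjects. The documents do not give the arm of the four cases. At most 2 can be placebo, so active cases = 4 - (0, 1 or 2) = 4, 3 or 2.
- If every elevation is recorded: 4/6 = 66.7%, 3/6 = 50.0% or 2/6 = 33.3%.
- If none is recorded: 0/6.

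The choice of rule thus moves the dose column by 33.3 to 66.7 percentage points. Any placebo case goes to the pooled placebo column.

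**5. Check whether another SAP output supplies the count.** SAP 15.3 summarises values and changes and lists abnormal results. It contains no table of subjects by dose with ALT, AST or bilirubin above any limit. Protocol 8.5.2.1 mentions post-dose shifts relative to baseline, but SAP 15.3 does not turn this into a table, and SAP section 7 does not list it as a change.

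**The case against.** The strongest reply is that the two rules are sequential and do not conflict. Since 7.4.1.2 makes AESIs a subset of AEs, the laboratory-finding rule decides what is an AE, and the AESI list decides which AEs get expedited reporting. That reading is coherent, but no text adopts it. It also leaves the liver AESI resting, for asymptomatic Part A cases, on judgement without a threshold. The eCRF completion conventions cited in 7.4.1.2 may contain a criterion. They are not among the documents, and the SAP does not refer to them.

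A second reply is that the data are not lost. This stands. SAP 15.3 lists every abnormal value, the SMC receives laboratory data directly (5.2.8), and the dose change in 5.2.2 followed graded enzyme values, not AESI counts. The exposure is limited to the AESI and TEAE tables and the 24-hour forms. Listings, however, do not give an incidence by dose.

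A reader might go further in three ways that the documents do not support:
- **That asymptomatic laboratory abnormalities are never AEs.** The rule has three limbs, and the SMC's response to the 1,000 mg rises makes a medically important reading plausible.
- **That the report will show 0 of 8 or 4 of 8.** Zero requires that none of the four met any limb, which is not stated, and the SAP's dose column is out of 6.
- **That ULN is the entry limit throughout.** It applies to Parts A and B only.

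**Conclusion.** The point holds as a gap in definition and counting, and it should be closed. Neither document gives a laboratory criterion for the liver AESI or says how it relates to the laboratory-finding rule, and the SAP supplies no other count of affected subjects by dose. For the one cohort with reported rises, the recorded number can be anything from 0 to 4 of 8. In the active-dose column this is 0/6 at one extreme and 2/6 to 4/6 at the other.

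The range assumes that the eight were allocated 6:2 as planned. Its lower end also assumes that none of the four was symptomatic or judged medically important. These are bounds on what the text permits, not a prediction of what was recorded. Safety review and dose decisions based on laboratory values are not shown to be affected.

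**What to change.** **Protocol 7.4.1.1 (and 7.4.4.7).** State that the symptom and discretion restriction does not govern the liver AESI, and name one laboratory criterion for it. The value is for the sponsor to set. A one-grade worsening may look natural, but at 1,000 mg it would count the same four subjects as any value above ULN, so it does not settle the choice.

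**SAP 15.2.3 and 15.3, before database lock and unblinding.** Derive from the collected laboratory data the number and percentage of dosed subjects by worst post-dose ALT, AST and bilirubin grade relative to baseline, by dose with placebo pooled. Show this alongside the recorded-AESI table. Use the toxicity scale already applied in 5.2.2 and write its laboratory cut-points into the SAP, since the grade descriptions in 7.4.1.1 are clinical only. Say whether unscheduled samples count, because SAP section 9 generally leaves them out of summaries.

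**Cost.** A sentence or two in the protocol, one derived variable and one table in the SAP, and possibly a few more AESI forms. No new assessments are needed, and the derivation covers cohorts already completed. SAP 6.2 requires approval of the plan before lock and unblinding, so the rule can be fixed in time.

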7.4.1.2 Methods of Recording and Assessing Adverse Events

At each trial visit, the subject will be queried on changes in his or her condition. During the reporting period, any unfavorable changes in the subject's condition will be recorded as AEs, whether reported by the subject or observed by the Investigator.

Complete, accurate, and consistent data on all AEs experienced for the duration of the reporting period (defined below) will be reported on an ongoing basis in the appropriate section of the eCRF. Among these AEs, all SAEs and all nonserious AESIs must be additionally documented and reported using a Serious Adverse Event Report Form as described in Section 7.4.1.4.

It is important that each AE report include a description of the event, its duration (onset and resolution dates [and times, when it is important to assess the time of AE onset relative to the recorded treatment administration time]), its severity (according to the QTS as described in the “Toxicity Grading Scale for Healthy Adult and Adolescent Volunteers Enrolled in Preventive Vaccine Clinical Trials”), its causal relationship with the IMP or rescue medication, any other potential causal factors, any treatment given or other action taken (including dose modification or discontinuation of the IMP), and its outcome. In addition, serious cases should be identified and the appropriate seriousness criteria documented.

Specific guidance can be found in the eCRF Completion and Monitoring Conventions provided by the CRO in coordination with of the Sponsor.

7.4.1.3 Definition of the Adverse Event Reporting Period

The AE reporting period for safety surveillance begins when the subject is initially included in any part (Part A, B, or C) of the trial (date of first signature of informed consent/date of first signature of first informed consent) and continues until the End of Trial visit (Day 44 ± 2 days) for the subject.

7.4.1.4 Procedure for Reporting Serious Adverse Events, Adverse Events of Special Interest and Dose Limiting Toxicities

Serious Adverse Events

In the event of any new SAE occurring during the reporting period, the Investigator must immediately (within a maximum of 24 HOURS after becoming aware of the event) inform the Sponsors, both Funding and the Local Sponsor, or their designee by fax or by e-mail. All written reports should be transmitted using the SAE Report Form, which must be completed by the Investigator following specific completion instructions.

When an SAE (or follow-up information) is reported by telephone, a written report must be sent immediately thereafter by fax or e-mail. Reporting procedures and timelines are the same for any new follow-up information on a previously reported SAE.

Names, addresses, telephone-, and fax numbers for SAE reporting will be included in the trial-specific SAE Report Form.

All written reports should be transmitted with the SAE Report Form, which must be completed by the Investigator following specific completion instructions.

Relevant pages from the eCRF may be provided in parallel (for example, medical history, concomitant drugs). Additional documents may be provided by the Investigator, if available (for

example, laboratory results, hospital report, autopsy report). In all cases, the information provided on the SAE Report Form must be consistent with the data on the event that are recorded in the corresponding section of the eCRF.

The Investigator must respond to any request for follow-up information (for example, additional information, outcome, final evaluation, other records where needed) or to any question the Sponsors/designees may have on the AE within the same timelines as those noted above for initial reports. This is necessary to ensure prompt assessment of the event by the Sponsor or designee and (as applicable) to allow the Sponsors to meet strict regulatory timelines associated with expedited safety reporting obligations.

Requests for follow-up will usually be made via the responsible Monitor, although in exceptional circumstances the Global Patient Safety department may contact the Investigator directly to obtain further information or to discuss the event.

Adverse Events of Special Interest

In the event of a *nonserious* AESI, the Investigator will complete the AESI Report Form and send it to the Sponsors/designees within a maximum of 24 HOURS after becoming aware of the event. Names, addresses, telephone-, and fax numbers for AESI reporting will be included on the Report Form. Serious AESIs have to be reported in an expedited manner as SAEs as outlined above.

7.4.1.5 Safety Reporting to Health Authorities, Independent Ethics Committees/ Institutional Review Boards and Investigators

The Local Sponsor will send appropriate safety notifications to the Local Health Authorities (Therapeutic Goods Administration) in accordance with applicable laws and regulations.

The Investigator must comply with any applicable site-specific requirements related to the reporting of SAEs (particularly deaths) involving trial subjects to the HREC that approved the trial.

In accordance with ICH GCP, the Sponsors/designees will inform the Investigator of “findings that could adversely affect the safety of subjects, impact the conduct of the trial or alter the HREC’s approval/favorable opinion to continue the trial.” In particular and in line with respective regulations, the Sponsors/designees will inform the Investigator of AEs that are both serious and unexpected and are considered to be related to the administered product (“suspected unexpected serious adverse reactions”). The Investigator should place copies of Safety Reports in the Investigator Site File. National regulations with regard to Safety Report notifications to Investigators will be taken into account.

When specifically required by regulations and guidelines, the Sponsors/designees will provide appropriate Safety Reports directly to the concerned lead HREC and will maintain records of these notifications. When direct reporting is not clearly defined by national or site-specific regulations, the Investigator will be responsible for promptly notifying the concerned HREC of any Safety Reports provided by the Sponsors/designees and of filing copies of all related correspondence in the Investigator Site File.

